10.6 Appendix 6: Study-Specified Opportunistic Infections

The study-specified opportunistic infections that will be monitored in this study are provided in Table 7.

Table 7 Study-Specified Opportunistic Infections

Definite ^{a,b} Opportunistic Infection	Probable ^c Opportunistic Infection
Pneumocystis jirovecii	Paracoccidioides infections
BK virus disease, including polyomavirus-associated nephropathy	Penicillium marneffei (talaromyces)
CMV disease	Sporothrix schenckii
Post-transplant lymphoproliferative disorder (EBV)	Cryptosporidium species (chronic disease only)
Progressive multifocal leukoencephalopathy	Microsporidiosis
Bartonellosis (disseminated disease only)	Leishmaniasis (visceral only)
Blastomycosis	Trypanosoma cruzi infection (Chagas's disease) (disseminated disease only)
Toxoplasmosis	Campylobacteriosis (invasive disease only)
Coccidioidomycosis	Shigellosis (invasive disease only)
Histoplasmosis	Vibriosis (invasive disease due to Vibrio vulnificus)
Aspergillosis (invasive disease only)	HCV progression
Candidiasis (invasive disease or pharyngeal)	
Cryptococcosis	
Other invasive fungi: Mucormycosis (zygomycosis) (Rhizopus , Mucor , and Lichtheimia), Scedosporium/Pseudallescheria boydii , Fusarium	
Legionellosis	
Listeria monocytogenes (invasive disease only)	
TB	
Nocardiosis	
Non-tuberculous mycobacterium disease	
Salmonellosis (invasive disease only)	
HBV reactivation	
Herpes simplex (invasive disease only)	
Herpes zoster (any form)	
Strongyloides (hyperinfection syndrome and disseminated forms only)	

CMV = cytomegalovirus; EBV = Epstein-Barr virus; HBV = hepatitis B virus; HCV = hepatitis C virus;

TB = tuberculosis

- a Generally does not occur in the absence of immunosuppression, but whose presence indicates a potential or likely alteration in host immunity.
- b Can occur in subjects without recognized forms of immunosuppression, but whose presence indicates a potential or likely alteration in host immunity.
- c Published data are currently lacking, but expert opinion believes that risk is likely elevated in the setting of biologic therapy.

Source: [Winthrop et al, 2015](#)

10.7 Appendix 7: Prednisone Equivalent of Oral Glucocorticoid Dose

Oral GCs other than prednisone may be used PO at the equivalent doses shown in Table 8.

A large black rectangular redaction box covers the majority of the page content, from approximately y=113 to y=300. The box is bounded by a thin white border and is positioned within a white rectangular frame.

10.8 Appendix 8: Recommended Oral Glucocorticoid Tapering Schedule

To provide guidance to Investigators, a recommended OGC tapering regimen is provided in Table 9.

Table 9 Recommended Oral Glucocorticoid Tapering Schedule

Visit	Dose of Oral Prednisone or Equivalent at Start of Study ^a				
Week 0	40 mg	30 mg	20 mg	10 mg	7.5 mg ^b
Week 4	30 mg	22.5 mg	15 mg	7.5 mg	5 mg
Week 8	20 mg	15 mg	10 mg	5 mg	4 mg
Week 12	12.5 mg	10 mg	7.5 mg	4 mg	3 mg
Week 16	7.5 mg	7.5 mg	5 mg	3 mg	2 mg
Week 20	5 mg	5 mg	4 mg	2 mg	1 mg
Week 24	4 mg	4 mg	3 mg	1 mg	Discontinue
Week 28	3 mg	3 mg	2 mg	Discontinue	Discontinue
Week 32	2 mg	2 mg	1 mg	Discontinue	Discontinue
Week 36	1 mg	1 mg	Discontinue	Discontinue	Discontinue
Week 40	Discontinue	Discontinue	Discontinue	Discontinue	Discontinue
Week 44	Discontinue	Discontinue	Discontinue	Discontinue	Discontinue
Week 48	Discontinue	Discontinue	Discontinue	Discontinue	Discontinue

OGC = oral glucocorticoid

The OGC tapering schedule represents an example of a tapering regimen to provide guidance to Investigators in the approach to steroid taper throughout the study with the aim to lower the daily dose OGC to total discontinuation if clinically possible throughout the study.

a Specified prednisone dose is dose at the beginning of the week.

b Subjects entering study at < 7.5 mg/day dose of OGC must taper until full discontinuation if clinically possible. It is encouraged that Investigators taper each month by at least 1 mg/day.

1 INTRODUCTION

This document describes the statistical analysis for protocol HZNP-DAX-204, an open-label extension study to evaluate the long-term safety and tolerability of daxdilimab (HZN-7734) in participants with systemic lupus erythematosus (SLE).

2 TRIAL OVERVIEW

2.1 Trial Objectives and Endpoints

The objectives and corresponding endpoints are listed in Table 1 below:

Table 1 Primary, Secondary, and Exploratory Objectives

Objectives	Endpoints		
Primary Objective			
To evaluate the long-term safety and tolerability of 200 mg Q12W daxdilimab	Incidence of AEs, SAEs, and AESIs		
Secondary Objectives			
To characterize the PK, PD, and immunogenicity of daxdilimab	Daxdilimab concentrations, change in pDCs, and ADA rate		
Exploratory Objectives			
ADA = anti-drug antibodies; AE =	= adverse event; AESI = AE of special interest; PD =		
pharmacodynamic(s); pDC = plasmacytoid dendritic cell; PGA = Physician Global Assessment; PK,			
pharmacokinetic(s); Q12W = every 12 weeks; RECAST SLE = Phase 2 Randomized, Double-Blind, Placebo- Controlled Efficacy and Safety Study of daxdilimab for the Treatment of Moderate to Severely Active			

Systemic Lupus Erythematosus;

SAE = serious AE; SLE = systemic

lupus erythematosus; SLEDAI-2K = Systemic Lupus Erythematosus Disease Activity Index 2000.

2.2 Trial Design

This is an open-label study designed to evaluate the long-term safety and tolerability of daxdilimab in participants completing the treatment period of the VIB7734.P2.S1 (RECAST SLE) clinical study. Once a participant has completed the treatment period (through Week 48) of the RECAST SLE study, signed the informed consent form, and met all study

eligibility criteria, he/she may be enrolled in this open label extension (OLE) study. Irrespective of their assigned treatment in the RECAST SLE study, all participants participating in the SLE OLE will be treated with daxdilimab 200 mg SC Q12W in addition to their standard-of-care SLE therapy for 48 weeks. After the treatment period (Week 0 to Week 48), the participants will enter an 8-week safety follow-up (SFU) period (Week 48 to Week 56). The basic study flow diagram is presented in Figure 1. Refer to Protocol for detailed trial design.

[figure not shown]

Figure 1 Study Flow Diagram

2.3 Sample Size Determination

Sample size determination is based on the number of participants who have completed the treatment period of Study VIB7734.P2.S1 (RECAST SLE). A total of 195 participants have been randomized in the RECAST SLE study. Assuming that 20% of participants will prematurely discontinue treatment, there will be a total of approximately 156 participants who will be eligible for this long-term safety study.

3 PLANNED ANALYSES

3.1 Final Analysis

The final analysis will be performed when all participants have completed trial.

4 STATISTICAL METHODS

4.1 General Considerations for Data Analyses

All statistical calculations will be primarily performed using SAS[®] System Version 9.4 or higher. Analysis results will be presented using descriptive statistics. For categorical variables, the number and percentage of participants in each category will be presented; for continuous variables, the number of participants (n), mean, standard deviation (SD), median, first quartile (Q1), third quartile (Q3), minimum, and maximum will be presented.

For additional details on data presentation, refer to the Statistical Programming Plan (SPP).

4.1.1 Definition of Baseline

Unless otherwise specified, baseline is defined as the last non-missing valid observation prior to the first dose of investigational product (IP) in Study RECAST SLE. In cases where baseline measurements are taken on the same day as IP and no times are reported, it will be assumed that these measurements are taken prior to IP being administered.

For immunogenicity analyses, baseline is defined as the last non-missing valid observation prior to the first dose of daxdilimab (either in OLE or RECAST SLE study).

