4.4 Analysis Sets

4.4.1 OLE Safety Analysis Set

The OLE safety analysis set is defined as participants who received any dose of daxdilimab in this OLE study. The OLE safety analysis set will be used for the safety and pharmacodynamics (PD) analyses.

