4.9.2 Clinical Laboratory Evaluations

The following summary will be provided for hematology, coagulation, chemistry, and lipid profile parameter for the OLE safety analysis set using the OLE data.

- Observed values and changes from the baseline by visit
- Worst toxicity grade
- \geq grade 3 toxicity post-baseline
- Shift from the baseline relative to the normal range
- Shift from baseline to worst toxicity grade

In addition, the number and percentage of participants with the following liver-related abnormalities will be summarized if meet the following criteria at any post-baseline visit.

- AST or ALT: (a) $\ge 3 \times ULN$; (b) $\ge 5 \times ULN$; (c) $\ge 8 \times ULN$
- Total bilirubin: $\geq 2 \times ULN$
- ALT or AST \geq 3 x ULN and total Bilirubin \geq 2 × ULN
- ALT or $AST \ge 5 \times ULN$ for more than 2 weeks

The following summary will be provided for urinalysis.

- Observed values and changes from the baseline
- Shift from the baseline relative to the normal range

Observed values and changes from baseline will be summarized descriptively for highsensitivity C-reactive protein (hs-CRP) and immunoglobulins parameters.

Listings will be provided for all clinical laboratory evaluations collected in this OLE study.

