4.9.3 Vital Signs

The observed values, along with the changes from baseline, will be summarized for systolic blood pressure, diastolic blood pressure, body temperature, heart rate, and respiratory rate using the OLE safety analysis set based on OLE data. In addition, a summary of participants with clinically significant vital signs values (meeting any of following criteria) will also be provided.

- Systolic blood pressure: < 90 mmHg, > 160 mmHg
- Diastolic blood pressure: < 60 mmHg, > 100 mmHg
- Heart rate: < 50 beats/min, > 100 beats/min

- Respiratory rate: < 12 breaths/min, > 23 breaths/min
- Temperature: < 36°C, >38°C

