4.9.5 Electrocardiogram Results

The observed values, along with the changes from baseline, will be summarized for ventricular heart rate, PR interval, QRS duration, QT interval, and the corrected QT interval (QTc) using the OLE safety analysis set based on OLE data. The number (%) of participants meeting the following criteria will be summarized:

- QTc > 450 msec
- QTc > 480 msec
- QTc > 500 msec
- QTc increases from baseline > 30 msec
- QTc increases from baseline > 60 msec

Corrected QT (QTc) intervals will be derived using Fridericia's correction (QTcF) and Bazett's correction (QTcB). In addition, the overall clinical evaluation of electrocardiogram results (normal, abnormal, not clinically significant abnormal, clinically significant abnormal) will also be summarized. Listings will be provided for all electrocardiograms results collected in this OLE study.

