4.9.6.2 Physical Examination and Weight

The observed values and the changes from baseline in the weight and body mass index (BMI) will be summarized using the OLE safety analysis set based on OLE data.

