4.11 Pharmacodynamics

The observed count along with the change and percent change from baseline in pDCs will be summarized descriptively using the OLE safety analysis set based on OLE data.

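### Change from baseline in labs, vital signs, ECG, weight/BMI and pDCs starts before the first RECAST dose, so for former-placebo participants it includes about 48 weeks without daxdilimab

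*SAP*

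**What the plan says.** SAP 4.1.1 gives one general rule, applying unless otherwise specified: "baseline is defined as the last non-missing valid observation prior to the first dose of investigational product (IP) in Study RECAST SLE". It then makes a single exception: "For immunogenicity analyses, baseline is defined as the last non-missing valid observation prior to the first dose of daxdilimab", counting a first dose in either study.

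The population for the affected analyses is set in SAP 4.4.1: "The OLE safety analysis set will be used for the safety and pharmacodynamics (PD) analyses". The sections that use a baseline are:

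- **Laboratory (SAP 4.9.2):** changes by visit, shifts to worst toxicity grade, and "Shift from the baseline relative to the normal range".
- **Vital signs (SAP 4.9.3):** "The observed values, along with the changes from baseline, will be summarized for systolic blood pressure" and the other vital signs.
- **ECG (SAP 4.9.5):** changes, plus counts of participants above thresholds such as "QTc increases from baseline > 60 msec".
- **Weight and BMI (SAP 4.9.6.2):** "changes from baseline in the weight and body mass index (BMI) will be summarized using the OLE safety analysis set based on OLE data".
- **pDCs (SAP 4.11), a named secondary endpoint:** "the change and percent change from baseline in pDCs will be summarized descriptively using the OLE safety analysis set based on OLE data".

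None of these sections defines a baseline of its own. Protocol 9.3.2.1 and 9.3.3.3 also refer to baseline without defining it.

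**The concern.** Under inclusion criterion 2 (Protocol 5.1), participants received either daxdilimab or placebo in RECAST. For those on daxdilimab, the value before the first RECAST dose is a true pre-drug value. For those on placebo it is not, because their first daxdilimab dose is OLE Day 1, which Protocol 4.1 places at RECAST Week 48. Their change from baseline mixes about 48 weeks on placebo and background therapy with whatever happens after daxdilimab starts.

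A QTc rise or laboratory shift that arose on placebo can thus appear in an OLE table as a change during the study. The pDC percent change in this group does not measure change since starting drug, although Protocol 4.3 gives pDC depletion and recovery under 12-weekly dosing as part of the dose rationale. The visible SAP text does not split these tables by RECAST arm, so a reader could not separate the two groups.

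There is a related literal problem. Under the default rule, the pre-dose OLE Day 1 value of a former-placebo participant counts as post-baseline. SAP 4.9.2 counts Grade 3 or higher toxicity and liver abnormalities post-baseline, so an abnormality found before any daxdilimab could be included. The statistical programming plan (SPP) may prevent this, but it is not available to check.

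The SAP recognises the issue elsewhere. It anchors ADA (4.1.1) and the combined TEAE definition (4.9.1) to the first daxdilimab dose, and 4.9.1 adjusts AE rates because former-placebo participants have shorter exposure.

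**Working it through.** **The plan's own figure.** SAP 2.3 gives 195 randomized and 20% premature discontinuation: 195 × (1 − 0.20) = 156. This reproduces the stated figure.

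**Age of the baseline.** The RECAST treatment period runs through Day 337 (Protocol 5.1): (337 − 1)/7 = 48 weeks. OLE Day 1 coincides with that visit. For a former-placebo participant at OLE Week *w*, the change spans 48 + *w* weeks, and the share before any daxdilimab is 48/(48 + *w*).

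| OLE week | Weeks since default baseline | Share before any daxdilimab | Weeks since first daxdilimab dose |
|---|---|---|---|
| Day 1, pre-dose | 48 | 100% | 0 |
| 12 | 60 | 80% | 12 |
| 24 | 72 | 67% | 24 |
| 36 | 84 | 57% | 36 |
| 48 | 96 | 50% | 48 |
| 56 | 104 | 46% | 56 |

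This is the age of the reference value, not the size of a bias. The 48 weeks is approximate: visit windows apply, the baseline value may precede the first RECAST dose, and the Medical Monitor may approve later enrollment.

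**How many participants.** The RECAST allocation ratio is not in the documents. Assuming a placebo share of 25% or 50% among 156: 156 × 0.25 = 39 and 156 × 0.50 = 78.

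**Illustration for mean percent change in pDCs.** All of these inputs are assumptions:

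- *r* = mean OLE Day 1 level divided by the RECAST baseline in former-placebo participants, taken as 0.7 to 1.3
- *d* = true change since the first daxdilimab dose, the same in both groups
- *p* = share of participants from placebo

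Former-placebo mean as planned = *r*(1 + *d*) − 1.
Pooled mean as planned = *p*[*r*(1 + *d*) − 1] + (1 − *p*)*d*.
The pooled shift from the true value is therefore *p*(*r* − 1)(1 + *d*).

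Worked case, *d* = −0.5, *r* = 0.7, *p* = 0.25: former-placebo 0.7 × 0.5 − 1 = −65%; pooled 0.25 × (−0.65) + 0.75 × (−0.50) = −53.75%.

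| True change *d* | Former-placebo alone (*r* = 0.7 / 1.3) | Pooled, *p* = 0.25 | Pooled, *p* = 0.50 |
|---|---|---|---|
| −50% | −65% / −35% | −53.75% / −46.25% | −57.5% / −42.5% |
| −90% | −93% / −87% | −90.75% / −89.25% | −91.5% / −88.5% |

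The planned pooled mean moves by 3.75 to 7.5 percentage points at a true −50%, and by 0.75 to 1.5 points at a true −90%. The wider former-placebo range describes a row that the visible SAP does not tabulate.

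**Is a usable value already collected?** Yes. The Schedule of Activities (Protocol Table 1) has ECG, vital signs and weight, hematology and chemistry, coagulation, lipids and pDCs at Visit 1, and Protocol 8.1 places all Day 1 assessments before dosing.

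**The case against.** The strongest objection is that the sections in question restrict themselves to OLE data. Since the general rule yields to any other specification, a programmer might read that as calling for an OLE value as baseline. The wording is ambiguous, and that is itself a reason to clarify it. Still, the phrase selects which records are summarized and does not define a reference point. Read as OLE Day 1 for everyone, it would give former-daxdilimab participants an on-drug baseline. The default remains the better reading.

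Second, the choice may be deliberate. A pre-RECAST value is a legitimate common reference for change since entry to the parent trial, and nothing in the protocol contradicts it. That stands, but it does not supply change on drug for this group.

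Third, much information survives. Observed values are tabulated, all OLE laboratory and ECG results are listed, and clinically significant abnormalities are also recorded as AEs (Protocol 9.3.2.1). The SPP, to which SAP 4.1 defers presentation detail, may add columns by RECAST arm. This limits the gap. Individual shifts and QTc-increase counts would still use the old baseline even with such columns.

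Fourth, the pDC figures rest on assumed inputs, and no figure can be offered for laboratory tests, QTc, vital signs or weight. That is correct, and the figures should be read only as an illustration.

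**Conclusion.** The point holds. Followed as written, the SAP gives former-placebo participants change, shift, QTc-increase and pDC results that do not measure change since starting daxdilimab. About 48 weeks of each interval precede the drug, which is 80% of the interval at OLE Week 12 and 46% at Week 56. At an assumed placebo share of 25% to 50%, 39 to 78 of 156 participants are concerned. The direction and size of any distortion in the actual data cannot be determined from the documents.

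The consequence is moderate. The AE, SAE and AESI primary endpoint, the observed values, the absolute-limit counts after Day 1, and the baselines of former-daxdilimab participants are unaffected. No hypothesis is tested (SAP 4.3). What is affected is one named secondary endpoint and the supportive safety tables. The change should be made, but the trial does not depend on it.

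**What to change.** In SAP 4.1.1, apply the rule already written for immunogenicity to laboratory tests, vital signs, ECG, weight/BMI and pDCs: the last valid value before the first daxdilimab dose in either study. State that for former-placebo participants the pre-dose OLE Day 1 value is the baseline and is not counted as post-baseline. Keep the pre-RECAST baseline for exploratory efficacy. Present the change, shift, QTc-increase and pDC tables by RECAST treatment group as well as overall, as SAP 4.9.1 already does for combined AEs.

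The cost is SAP wording, one additional baseline flag and a few more tables, with no new visits or data. The drawback is that overall rows would pool baselines of different age, which is why the by-group tables are needed. If one common baseline is preferred for the overall rows, a supplementary table of change from OLE Day 1 for former-placebo participants would supply the same information.

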4.1.2 Analysis Windows

Analysis visit windows will be used for all visit-based assessments to map longitudinal observations to scheduled visits and thereby allow for by-visit analyses, since not all assessments are performed on the scheduled day. Unless otherwise specified, all longitudinal efficacy, safety, and biomarker data analyses will be based on the analysis visit windows.

The analysis visit windows will be calculated by bisecting the interval between adjacent scheduled visit days except for the first post-treatment visits of the RECAST SLE study and OLE study, and the Week 48 visit. The detailed analysis visit windows will be specified in SPP.

The actual assessment day will be mapped to the windows defined for each scheduled study visit with following rules:

- If more than one assessment falls within a visit window, the closest non-missing assessment to the scheduled day will be used in the analysis.
- If 2 non-missing assessment actual dates are equidistant from the target day, the later visit will be used in the analysis.
- For retest values of laboratory data, the retest value will be chosen.

All observations will be included in data listings.

4.1.3 Missing Data

In general, missing data will not be imputed unless methods for handling missing data are specified.

4.2 **Protocol Deviations**

The protocol deviations are reviewed and categorized as major and minor prior to the database lock. The number and percentage of participants with major protocol deviations by deviation reason (eg, nonadherence to study drug, violation of select inclusion/exclusion criteria) will be summarized. A by-participant listing will be provided for all protocol deviations.

A by-participant listing will be provided for those participants who did not meet at least one eligibility (inclusion or exclusion) criterion. The listing will present the eligibility criterion (or criteria if more than one deviation) that participants did not meet and related comments, if collected.

4.3 **Primary Hypothesis**

No formal statistical hypothesis will be evaluated.

4.4 Analysis Sets

4.4.1 OLE Safety Analysis Set

The OLE safety analysis set is defined as participants who received any dose of daxdilimab in this OLE study. The OLE safety analysis set will be used for the safety and pharmacodynamics (PD) analyses.

4.4.2 Full Analysis Set

The full analysis set is defined as participants who were randomized and received any dose of IP in study RECAST SLE. Participants will be analyzed according to the treatment to which they were randomized in RECAST SLE study. The exploratory efficacy analyses will be based on the full analysis set.

4.4.3 Any Daxdilimab Analysis Set

The any daxdilimab analysis set includes all participants who receive at least one dose of daxdilimab in study RECAST SLE or this OLE study. The any daxdilimab analysis set will be used for the adverse events and immunogenicity analyses.

4.4.4 Pharmacokinetic Analysis Set

The PK analysis set is defined as participants who received any dose of daxdilimab in this OLE study and have at least one measurable PK concentration post dose. The PK analyses will be based on PK analysis set.

4.5 **Participant Disposition**

A summary of participant disposition will be presented for the full analysis set using the categories presented below.

- Completed Week 48 in RECAST SLE
- Enrolled in OLE
- Enrolled but not treated
- Enrolled and treated
- Completed treatment
- Discontinued treatment with reasons
- Completed trial
- Discontinued trial with reasons

